## 12.1.15. Prior and Concomitant Medications

All concomitant medications will be recorded from the time the patient signs the informed consent form through 30 days after the last dose of study drug.

## 12.1.16. Adverse Event Assessments

Information regarding the occurrence of AEs and SAEs will be collected from the time the patient signs the informed consent form throughout their participation in the study, including a period of 30 days after the patient's last dose of study drug, unless a new treatment has been

started. Any known untoward event that occurs beyond the AE reporting period that the investigator assesses as possibly related to tesevatinib also should be reported to Kadmon.

**Note:** AEs resulting in a patient's permanent discontinuation from the study, regardless of seriousness or relationship to study drug, MUST be promptly reported to the sponsor.

#### 12.1.17. Study Diary

Patients will be required to keep a study drug diary in which they will record the date and time that each dose of tesevatinib is taken as well as any missed doses. Diaries will be reviewed at each visit during the treatment periods.

#### 12.2. Schedule of Visits

#### 12.2.1. Screening Visit

At the screening visit (Day -22 to -1), information will be collected and patients will have clinical evaluations as follows:

- Informed consent
- Medical history
- Demographics
- Vital sign measurements (sitting blood pressure, heart rate, respiratory rate, temperature)
- Neurological examination
- Tumor sample; original tumor and any subsequent biopsies required
- Inclusion/exclusion criteria
- Complete physical examination, including height and weight
- Hematology, cystatin-C, serum chemistry, coagulation, and urinalysis
- Urine pregnancy test, if applicable. Subject must have a negative urine pregnancy test documented within the 24-hour period prior to the first dose of study drug. Positive results are to be confirmed with serum testing.
- Supine 12-Lead ECG (repeat three times consecutively within 30 minutes [must have an interval of at least 1–2 minutes between ECGs]; perform ECG immediately prior to blood sample collection when possible)
- Disease assessment (MRI, clinical status, and corticosteroid use) within 7 days before study drug administration
- Baseline AE assessment
- Baseline concomitant medications

#### 12.2.2. Cycle 1; Day 1

Results of clinical and laboratory evaluations, including ECGs, must be reviewed prior to dosing to confirm that the patient continues to meet eligibility criteria. At the Day 1 Visit, the following procedures and evaluations will be performed:

- Vital sign measurements (predose and 1 and 4 hours postdose) (sitting blood pressure, heart rate, respiratory rate, temperature)
- Complete physical examination, including weight
- Clinical laboratory tests (hematology, cystatin-C, serum chemistry panel and urinalysis) (Need not be repeated if screening visit occurred within 4 days prior to Day 1 visit.)
- Urine pregnancy test, if applicable. Positive results are to be confirmed with serum testing.
- Supine 12-Lead ECG (to be performed predose, and 4 8 hours postdose prior to any blood sample collection) (repeat three times consecutively within 30 minutes [must have an interval of at least 1-2 minutes between ECGs])
- Tesevatinib administration
- Completion of PRO MDASI-BT
- Concomitant medications
- AE assessment
- Issue study drug diary
- Dispense study drug

## 12.2.3. Cycle 1; Day 15

At the Cycle 1, Day 15 visit ( $\pm$  3 days), the following evaluations will be performed:

- Vital sign measurements (predose and 1 and 4 hours postdose) (sitting blood pressure, heart rate, respiratory rate, temperature)
- Limited physical examination
- Clinical laboratory tests (hematology, cystatin-C, serum chemistry panel and urinalysis)
- Supine 12-Lead ECG (to be performed predose, and 4 8 hours postdose prior to any blood sample collection) (repeat three times consecutively within 30 minutes [must have an interval of at least 1-2 minutes between ECGs])
- Tesevatinib administration
- Plasma sample predose for tesevatinib concentration

- Concomitant medications
- AE assessment

#### 12.2.4. Cycle 2; Day 1

At the Cycle 2, Day 1 visit ( $\pm$  3 days), the following procedures and evaluations will be performed:

- Vital sign measurements (sitting blood pressure, heart rate, respiratory rate, temperature)
- Complete physical examination
- Clinical laboratory tests (hematology, cystatin-C, serum chemistry panel and urinalysis)
- Urine pregnancy test, if applicable. Positive results are to be confirmed with serum testing.
- Supine 12-Lead ECG (to be performed predose, and 4 8 hours postdose prior to any blood sample collection) (repeat three times consecutively within 30 minutes [must have an interval of at least 1-2 minutes between ECGs])
- Completion of PRO MDASI-BT
- Disease assessment (MRI, clinical status, corticosteroid use and overall disease assessment)
- Tesevatinib administration
- Plasma sample predose for tesevatinib concentration
- Concomitant medications
- AE assessment
- Issue study drug diary
- Dispense study drug

#### 12.2.5. Cycle 3; Day 1

At the Cycle 3, Day 1 visit ( $\pm$  3 days), the following procedures and evaluations will be performed:

- Vital sign measurements (sitting blood pressure, heart rate, respiratory rate, temperature)
- Complete physical examination
- Clinical laboratory tests (hematology, cystatin-C, serum chemistry panel and urinalysis)

- Urine pregnancy test, if applicable. Positive results are to be confirmed with serum testing.
- Supine 12-Lead ECG (to be performed predose, and 4 8 hours postdose prior to any blood sample collection) (repeat three times consecutively within 30 minutes [must have an interval of at least 1-2 minutes between ECGs])
- Neurological examination
- Plasma sample predose for tesevatinib concentration
- Disease assessment (MRI, clinical status, corticosteroid use and overall disease assessment)
- Tesevatinib administration
- PRO MDASI-BT
- Concomitant medications
- AE assessment
- Collect/Issue study drug diary
- Dispense study drug

#### 12.2.6. Cycle 4; Day 1

At the Cycle 4, Day 1 visit ( $\pm$  3 days), the following procedures and evaluations will be performed:

- Vital sign measurements (sitting blood pressure, heart rate, respiratory rate, temperature)
- Complete physical examination
- Clinical laboratory tests (hematology, cystatin-C, serum chemistry panel and urinalysis)
- Urine pregnancy test, if applicable. Positive results are to be confirmed with serum testing.
- Supine 12-Lead ECG (to be performed predose, and 4 8 hours postdose prior to any blood sample collection) (repeat three times consecutively within 30 minutes [must have an interval of at least 1-2 minutes between ECGs])
- Plasma sample predose for tesevatinib concentration
- Tesevatinib administration
- Concomitant medications
- AE assessment

- Collect/Issue study drug diary
- Dispense study drug

#### 12.2.7. Cycle 5; Day 1

At the Cycle 5, Day 1 visit ( $\pm$  3 days), the following procedures and evaluations will be performed:

- Vital sign measurements (sitting blood pressure, heart rate, respiratory rate, temperature)
- Complete physical examination
- Clinical laboratory tests (hematology, cystatin-C, serum chemistry panel and urinalysis)
- Urine pregnancy test, if applicable. Positive results are to be confirmed with serum testing.
- Supine 12-Lead ECG (to be performed predose, and 4 8 hours postdose prior to any blood sample collection) (repeat three times consecutively within 30 minutes [must have an interval of at least 1-2 minutes between ECGs])
- Neurological examination
- Plasma sample predose for tesevatinib concentration
- Disease assessment (MRI, clinical status, corticosteroid use and overall disease assessment)
- Tesevatinib administration
- PRO MDASI-BT
- Concomitant medications
- AE assessment
- Collect/Issue study drug diary
- Dispense study drug

#### 12.2.8. Cycle 6; Day 1

At the Cycle 6, Day 1 visit ( $\pm$  3 days), the following procedures and evaluations will be performed:

- Vital sign measurements (sitting blood pressure, heart rate, respiratory rate, temperature)
- Complete physical examination

- Clinical laboratory tests (hematology, cystatin-C, serum chemistry panel and urinalysis)
- Urine pregnancy test, if applicable. Positive results are to be confirmed with serum testing.
- Supine 12-Lead ECG (to be performed predose, and 4 8 hours postdose prior to any blood sample collection) (repeat three times consecutively within 30 minutes [must have an interval of at least 1-2 minutes between ECGs])
- Plasma sample predose for tesevatinib concentration
- Tesevatinib administration
- Concomitant medications
- AE assessment
- Collect/Issue study drug diary
- Dispense study drug

#### 12.2.9. Cycle 7-24; Day 1

At the Cycle 7+, Day 1 visit ( $\pm$  3 days), the following procedures and evaluations will be performed:

- Vital sign measurements (sitting blood pressure, heart rate, respiratory rate, temperature)
- Complete physical examination
- Clinical laboratory tests (hematology, cystatin-C, serum chemistry panel and urinalysis)
- Urine pregnancy test, if applicable. Positive results are to be confirmed with serum testing.
- Supine 12-Lead ECG (to be performed predose, and 4 8 hours postdose prior to any blood sample collection) (repeat three times consecutively within 30 minutes [must have an interval of at least 1-2 minutes between ECGs])
- Neurological examination
- Disease assessment (MRI, clinical status, corticosteroid use and overall disease assessment)
- Tesevatinib administration
- PRO MDASI-BT
- Concomitant medications
- AE assessment

- Collect/Issue study drug diary
- Dispense study drug

#### 12.2.10. Cycle 26+; Day 1

At the Cycle 26+, Day 1 visit ( $\pm$  3 days), the following procedures and evaluations will be performed:

- Limited physical examination
- Neurological examination
- Vital sign measurements (sitting blood pressure, heart rate, respiratory rate, temperature)
- Clinical laboratory tests (hematology and serum chemistry panel
- 12-Lead ECG
- Disease assessment (MRI, clinical status, corticosteroid use and overall disease assessment)
- Karnofsky performance status
- Concomitant medications
- Tesevatinib dispensing
- AE assessment

#### 12.2.11. Day 15 on Cycle 2 through Cycle 6

At the Day 15 visit of Cycles 2, 3, 4, 5, and 6 ( $\pm$  3 days), the following evaluation will be performed:

• Serum Chemistry (Cystatin C does not need to be tested)

## 12.2.12. End-of-Study Drug Treatment Visit (EOS)

As soon as possible after the last dose of study drug, patients are to return to the study site to complete all end-of-study drug treatment assessments as described below. This may occur at the visit at which disease progression is diagnosed.

• Vital sign measurements (sitting blood pressure, heart rate, respiratory rate, temperature)

- Complete physical examination
- Clinical laboratory tests (hematology, cystatin-C, serum chemistry panel and urinalysis)
- Urine pregnancy test, if applicable. Positive results are to be confirmed with serum testing.
- Supine 12-Lead ECG (to be performed predose, and 4 8 hours postdose prior to any blood sample collection) (repeat three times consecutively within 30 minutes [must have an interval of at least 1-2 minutes between ECGs])
- Disease assessment (MRI, clinical status, corticosteroid use and overall disease assessment) if not done within the previous 8 weeks. If PD was not observed prior to the EOS visit, disease assessments should be performed until PD.
- PRO MDASI-BT
- Concomitant medications
- AE assessment
- Collect study drug diary
- Collect study drug

#### **12.2.13. 30-Day Follow-up**

The 30-Day Follow-Up should occur 30 days ( $\pm$  5 days) after the patients' last dose of tesevatinib, but prior to starting new therapy. This may occur prior to 30 days if new therapy is started within 30 days of last dose of study drug.

- Vital sign measurements (sitting blood pressure, heart rate, respiratory rate, temperature)
- Complete physical examination
- Clinical laboratory tests (hematology, cystatin-C, serum chemistry panel and urinalysis)
- Urine pregnancy test, if applicable. Positive results are to be confirmed with serum testing.
- Concomitant medications
- If PD was not observed prior to the 30-day follow-up visit, disease assessments should be performed until PD.
- AE assessment

#### 12.2.14. Follow-up Phone Contact

Beginning 8 weeks after the 30-Day Follow-Up Visit, patients are to be contacted by telephone every 8 weeks to assess survival status and any subsequent anti-cancer treatment. If PD was not observed before the 30-day follow-up period patients will need to return for follow-up MRI until PD is demonstrated or they start a new anti-cancer treatment. In the case of a patient receiving a new anti-cancer treatment in the absence of PD, the date of the most recent MRI will be used as the date of PD.

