# 10. EFFICACY ASSESSMENTS

Disease assessments will be based on the RANO criteria [Wen 2010] and will comprise radiological assessments (MRI), clinical assessments (KPS), and corticosteroid use. Based on radiological assessments, clinical status, and corticosteroid use, an overall evaluation of CR, PR, SD, or PD should be made at each disease assessment after baseline according to the RANO criteria (Appendix 2).

Disease assessment during the screening period is to be performed within 7 days before study drug administration and must be used as the baseline radiological assessment. Per the study's schedule of assessments (see Table 1), disease assessment is intended to be done prior to starting cycle 2, 3, 5, 7+. The corticosteroid dose should be kept stable for 5 days prior to the MRI scan. During the study, disease assessments should be performed at week 4 and week 8 after the date of first study treatment and then every 8 weeks (at Week 16, 24, etc.), regardless of treatment delays. For patients who discontinue treatment for other reasons than PD, disease assessment in the follow-up period should continue every 8 weeks (according to the original schedule) until disease progression. For patients with PD, disease assessment at the EOS is only required if not performed within the previous 8 weeks.

Disease assessments as initially planned according to the schedule of assessments should be maintained regardless of treatment delays. Unscheduled disease assessments may be performed at the discretion of the investigator to allow a decision on further study treatment administration for individual patients. For patients who discontinue treatment for reasons other than progressive disease, disease assessment in the follow-up period should continue every 8 weeks (according to the original schedule) until disease progression.

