## 13.4.6. Efficacy/Activity

## **13.4.6.1.** Primary efficacy endpoint

## Progression-Free Survival at 6 months (PFS-6).

PFS is defined as the time between date of first dose and the date of first documented disease progression or death, whichever occurs first. The PFS-6 is defined as a patient being alive and progression free at 6 months (24 weeks). Disease progression will be determined based on investigator assessment with use of radiological assessments, clinical status, and corticosteroid

use. The specific criteria for disease progression is defined in Appendix 2. Patients without a date of disease progression or death will be analyzed as censored observations on the date of the last disease assessment; if no post-baseline disease assessment is available, PFS will be censored at the date of 1st dose.

The analysis of the primary endpoint and the estimation of PFS-6 is performed with a Cox model. Karnofsky performance status is included as a covariate. Study center is included as a random effect assumed to follow a gamma distribution. Thus, this is a shared Cox gamma frailty model. The model is used to estimate PFS-6 with 2-sided 95% and 90% confidence intervals.

Furthermore, Kaplan-Meier methodology will be used to estimate median PFS with 95% CI and the Kaplan-Meier curve will be constructed to provide a visual description of the PFS over time.

Descriptive statistics overall and for each parameter (radiological assessment, clinical status and corticosteroid dose) in the disease progression assessment are presented for the entire assessment period as well as for 3, 6 and 9-month time points.

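### New therapy without progression is dated as PD on the last scan that showed none; the SAP neither carries nor withdraws this rule

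*Protocol*

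**What the plan says.** Protocol 12.2.14 (Follow-up Phone Contact) sets the rule. Its condition is "In the case of a patient receiving a new anti-cancer treatment in the absence of PD", and its consequence is that "the date of the most recent MRI will be used as the date of PD". The Table 1 footnote on telephone contact (lettered q) repeats it.

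Protocol 13.4.6.1 defines the endpoint: "PFS is defined as the time between date of first dose and the date of first documented disease progression or death, whichever occurs first". A patient with no date of progression or death is censored at the last disease assessment, or at first dose if there was no assessment after baseline. PFS-6 is judged at 24 weeks.

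Two timing rules in Protocol section 10 determine where the most recent MRI can fall. For baseline: "Disease assessment during the screening period is to be performed within 7 days before study drug administration". On study: "disease assessments should be performed at week 4 and week 8 after the date of first study treatment and then every 8 weeks". Under 12.2.12, the end-of-treatment assessment may be omitted if one was done in the previous 8 weeks.

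The SAP has no new-therapy rule. Section 3.1.4.3 censors patients without an event at data cut-off or loss to follow-up. Section 3.8.1 takes the proportion alive and not progressed at 24 weeks, uses the RANO criteria in Protocol Appendix 2, and counts unknown status as failure. Section 3.1.2 says that the primary and secondary methods were changed from the protocol where necessary, without listing the changes.

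**The concern.** The rule applies only when no progression has been found. The scan that it selects is therefore the last imaging evidence that the patient was progression-free, and it becomes the date of progression. Nothing was documented on that scan, so the rule conflicts with a PFS definition that ends at documented progression. Elsewhere the protocol backdates progression only once later imaging has confirmed it: for equivocal scans (10.1), and for steroid increases (synopsis, Overall Disease Assessment). Here it backdates with no confirmation.

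At stake are event times that fall too early or are impossible and, if the protocol date reaches the primary analysis, PFS-6 successes recorded as failures. With 40 patients, one reclassified patient is visible in the result. DOR ends at progression and is exposed in the same way.

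**Working it through.** **Plan's own figures.** The documents give no figure for the effect of this rule, so the design figures are reproduced first.
- Interim (Protocol 13.3), at most 1 of 21 at a rate of 5%: 0.95^21 + 21 × 0.05 × 0.95^20 = 0.341 + 0.376 = 0.717, against the stated 72%.
- Power (Protocol 13.2), n = 40: the Weibull with S(4.5) = 0.50 and S(6) = 0.25 has shape 2.41 and scale 5.24 (Table 6 appears to print these under each other's label). In 20,000 simulated trials, PFS-6 was estimated by the Cox/Breslow method without covariates, with a log-log 90% lower limit. Power was 95.4% for an estimate above 15%, 95.4% against 7% and 81.5% against 10%. The plan states 95%, 95% and 80%.
- An exact binomial test against 10% needs at least 8 of 40 (one-sided alpha 0.042). Its power at 25% is 81.8%.

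**Date arithmetic.** Days are counted from first dose, so 24 weeks = 168 days.
1. *Negative time.* The baseline MRI lies between day -7 and day 0. If new therapy starts before the Week 4 scan, the baseline MRI is the most recent one, and PFS = MRI date - first dose = -7 to 0 days. SAS survival procedures do not use a negative time, so such a patient would drop out of the time-to-event analysis.
2. *Backdating.* After Week 8 the scans are 56 days apart, so the assigned date precedes the start of new therapy by up to 56 days. With ±3-day windows at both ends this is 56 + 3 + 3 = 62 days, and more if a scan is missed. Example: clean scan on day 112, new therapy on day 160. The event is dated 160 - 112 = 48 days before anything happened.
3. *Week 24.* Section 10 intends the scan before Cycle 7 Day 1 (day 168), and 12.2.9 gives that visit ±3 days. If the window also applies to the scan, it falls on days 165 to 171. If new therapy starts before the next scan, PFS equals the scan day. Days 165 to 167 give a failure. Day 168 gives a failure if PFS must exceed 168 days. Days 169 to 171 give a success at a 168-day cut.

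**One patient under each text.** Clean Week 24 scan on day 165 (study day 166), new therapy on day 190:

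| Text applied | PFS | PFS-6 |
|---|---|---|
| Protocol 12.2.14 date | event, day 165 | failure |
| Protocol 13.4.6.1, assigned date ignored | censored, day 165 | no event counted |
| SAP 3.1.4.3 and 3.8.1 alone | censored at cut-off or loss to follow-up | success, if the scan establishes status at 24 weeks |
| Event at start of new therapy | event, day 190 | success |

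**Size for PFS-6.** Each reclassified patient costs 1/40 = 2.5 points. Starting from the planned 10 of 40:

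| Reclassified | PFS-6 | Exact 90% lower limit | Clopper-Pearson 95% lower limit |
|---|---|---|---|
| 0 | 25.0% | 14.2% | 12.7% |
| 1 | 22.5% | 12.3% | 10.8% |
| 2 | 20.0% | 10.4% | 9.05% |
| 3 | 17.5% | 8.5% | 7.3% |

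The 90% limit matches the one-sided 5% test in the power statement. The 95% limit is the one that SAP 3.1.4.2 specifies.

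**Power, under an assumption.** If a fraction f of true 24-week successes is reclassified, the effective rate is 0.25 × (1 - f). For f = 5%, 10% and 20% this is 23.75%, 22.5% and 20%. Exact power against 10% falls from 81.8% to 76.7%, 70.6% and 56.3%. The documents give no value for f.

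**Interim.** If the rule is applied at the futility look, one such patient turns 2 of 21 (continue) into 1 of 21 (stop).

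**The case against.** The strongest reply is that the SAP governs and does not contain the rule. SAP 3.8.1 uses a RANO-based proportion, and Appendix 2 has no new-therapy criterion. A reader might infer that a clean Week 24 scan simply becomes a PFS-6 failure. The documents do not support that as a general statement. It needs the protocol PD date to be carried into the analysis, a scan on or before the cut, and new therapy before the next scan. This stands, but silence is not withdrawal: SAP 3.1.2 does not list its changes, so nothing shows that the protocol date is overridden.

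Second, the rule sits in long-term follow-up, which the synopsis says is no longer required as of Amendment 4. SAP 2.2 follows patients for 30 days or until new treatment. Section 9.3.2 also says that new anti-cancer treatment should wait for documented PD. The rule may therefore touch few patients. Even so, 12.2.14 and the footnote keep it, sections 10, 12.2.12 and 12.2.13 still ask for assessments until PD, and 12.2.13 foresees new therapy within 30 days of the last dose.

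Third, a reader might infer that PFS is always shortened by up to 8 weeks. That holds only against the start of new therapy, and 56 days is nominal. Against the censoring rule in 13.4.6.1, when the MRI is the last assessment, the time is unchanged and a censored time becomes an event. Nor does a shift in an affected patient's time translate into the same shift in median PFS.

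Fourth, the negative-time case is an edge case. It affects time-to-event PFS. In the SAP's proportion the patient stays in the denominator and would be a failure under the proposed rule too.

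Finally, the bias lowers PFS-6, so it is conservative for a claim of activity. That is correct, though it could also lead to an active drug being dropped.

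**Conclusion.** The point holds as a conflict that should be resolved. It is not a demonstrated loss of successes. The protocol dates progression to a scan that did not show it, which contradicts its own PFS definition and, read literally, permits times of -7 to 0 days. For the same patient the documents allow an event at the last MRI, censoring at the last assessment, or censoring at cut-off or loss to follow-up. The primary endpoint should not depend on which of these is programmed.

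If the protocol date is used, the cost is 2.5 points of PFS-6 per affected patient. From 10 of 40, three such patients take the exact 90% lower limit below the 10% comparison rate; on the SAP's 95% interval, two are enough. These counts are illustrations, because the documents give no rate of new therapy without progression and Amendment 4 may make it small. The direction is downward.

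**What to change.** Delete the most-recent-MRI dating from Protocol 12.2.14 and the Table 1 footnote. State one new-therapy rule in SAP 3.1.4.3 (PFS), 3.8.1 (PFS-6) and 3.8.2.5 (DOR), and make Protocol 13.4.6.1 agree with it.
- If new therapy without PD is kept as an event, date it to the start of the new therapy, never before first dose.
- For PFS-6, count it as a failure only if the new therapy started before the 24-week landmark.
- Report censoring at the last disease assessment, as in Protocol 13.4.6.1, as a sensitivity analysis.

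The cost is a few sentences and one extra analysis run. The sponsor should confirm that start dates of new therapy are still collected after Amendment 4, since the telephone contacts were the route for learning of later treatment. The small downside is that these dates may be incomplete for some patients.
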